Aim 1: Feasibility will be assessed through examination of participant recruitment, retention and engagement. Specifically, we will look at the number of participants who refuse to participate in the pilot at the time of recruitment and the reason they declined participation. Secondary impacts of interest include: medication adherence as measured by the four-item MA Questionnaire (MAQ) and change in systolic and diastolic blood pressure at 3 months.

Aim 2: To test the acceptability of a 3-month SMS-based intervention in adults with uncontrolled hypertension. One cohort of 24 participants will be recruited for the SMS intervention. Acceptability will be assessed using the systems usability scale (a validated questionnaire that measures usability reliably in small samples)¹⁸ and eliciting free comments after the survey.

At the end of this pilot project, we will have preliminary data essential for a future formal efficacy trial, to be proposed in a subsequent application to the AHRQ.

Our **first hypothesis** is that over 50% of contacted patients will respond to SMS messages and over 50% will check HBPM. This estimate is based on previous study by Bobrow and

colleagues in a similar patient population.³ Our **second hypothesis** will be that > 75% will be satisfied with the service (OK or above on the usability survey).⁹

Methods and Measures

Design

A randomized control trial of 24 non-adherent participants will be monitored and followed for 3 months; An ambulatory BP arm device will be provided to all participants with printed instructions in English or Spanish (from the American Heart Association) on how to measure BP at home (HBPM). Patients will be instructed on checking their BP at least twice a week.^{14,19} Text messages will be generated by Twilio platform, keeping a record of participants contacted, sent and received texts. Participants in the control arm will receive standard of care education for controlling high blood pressure in clinic by their healthcare providers. They will be followed to monitor any changes in their BP throughout the duration of the study.

Study team members will identify patients with uncontrolled hypertension during clinic visits. Study team members will approach patients 18 years or older who have uncontrolled HTN (SBP>130 or DBP >80) and have 2 or more BP medication(s) on their medication list.

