Participants will be interviewed by the study team and those with a MAQ score of 1 to 4 will be classified as non-adherent will be invited to participate. The study team member will assess the potential participant's phone ownership, text messaging ability, text messaging willingness, and receptivity to the intervention (and record all this information). The MAQ cut-off was chosen for the study because it has been used in the literature in previous studies,²⁰⁻²² and the cut-off at this value provides a highly sensitive tool for identifying medication non-adherence.^{22,23}

Participants will be randomized into one of two groups: intervention SMS arm or the control arm. If enrolled in the intervention arm, the subjects will be contacted by phone via SMS and phone call. To ensure equal access to participation among women and minorities we will translate all materials and questions to Spanish. The privacy of potential subjects during recruitment will be protected by collecting only necessary identifiers and using a private room during the interview process.

As part of routine care, patients who present to the office with uncontrolled HTN receive instructions from their clinician on medication changes and are advised to return for a nurse visit in 2 weeks and a clinician visit in 3 months. During follow-up, the nurse checks the patient's blood pressure and contacts the clinician for further management if the BP is not controlled. Participants in the SMS arm will receive SMS messages to monitor their blood pressure in addition to this routine care whereas the control arm will only receive the standard provider education and monitoring for controlling blood pressure.

Baseline demographic characteristics of the participants will be collected. Participants will be followed with office (or phone if they no show for their visit) interviews at 2 weeks or 3 months to complete 2 validated scales: the MAQ, and SUS+ free comments

Study intervention participants will be provided with a blood pressure monitor to be used for measurement and extraction of HBPM information. Clinicians will be alerted through an in-basket message in the electronic medical record (Wake One) if the participants report BP outside the threshold range, and the patient will be sent an SMS and prompted to contact their clinic. The threshold range set for SBP is between 90 and 180 mm Hg and between 60 and 110 mm Hg for DBP for one-time measurements. These thresholds are made based on the

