recommendations by HTN guidelines, which designate a hypertensive urgency to be 180/110 mm Hg or higher and hypotension 90/60 or lower.²

Patients who no show to the follow up visits will be telephoned to assess adherence barriers. The study team member will create a telephone encounter in the electronic health record to document their discussion and route it to the patient's PCP. Patients who refuse participation in the study will be asked for the reason and their responses will be recorded to determine any barriers to participation. Study team members will attempt to contact patients who miss follow up visits every week up to 3 times, if after the 3rd time the patient is still not able to be reached, the patient will be lost to follow up.

Setting

The study team will recruit patients who fall within the eligibility criteria from Wake Forest Baptist Medical Center.

Subjects selection criteria

Eligibility and recruitment

Inclusion criteria

Patients 18 years and older who have SBP>130 or DBP >80 during an office visit encounter in the past 6 months and have BP medication(s) on their medication list.

- Own a phone with SMS capability
- Non-adherent-MAQ score of 1 to 4
- Vulnerable population (Black, Hispanic or education level < or equal high school (as an indicator of low SES)

Exclusion Criteria

- End-stage renal disease (on hemodialysis or peritoneal dialysis)
- Kidney transplant recipients
- Unable to afford BP medications or lack transportation to clinic visits
- Hospice or nursing home care
- Dementia or cognitive impairment on the problem list

Sample Size

24 patients –We will randomize 12 patients into 2 groups

Interventions and Interactions

Pilot randomized controlled study.

Participants in the SMS intervention arm will receive usual care and SMS texting and phone calls. Study team members will send secure SMS messages to participants weekly for four weeks and then every other week until their next appointment.

The secure messaging system will be as follows

Introductory message:

Welcome to managing your blood pressure with the Nephrology/ Internal medicine clinics at Wake Forest. Try to take your BP meds at the same time every day to keep your BP under control! Make it part of your daily routine:

First week

Adherence checkpoint:

1. *Good morning! Did you take your blood pressure medications today?*

“No” Response:

1. *Let's try to stay on top of taking them daily! You can do this!*

Additional prompts:

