Did you fill your prescription?

- -If no -> phone call to determine barrier to filling BP meds “Mr./Mrs. (X). My name is (Y), we met when you were in the 7th Janeway clinic. I am calling you to find out if you are having difficulties filling your prescriptions. I will let Dr. (Name) know. Have you tried our pharmacy?” Message clinician in Wake One.
- If yes
- *Did you have any side effects from your blood pressure medication?*
- -If yes -> phone call to determine side effects
- Mr./Mrs. (X). My name is (Y), we met when you were in the 7th Janeway clinic. I am calling you to find out if you are having side effects from your blood pressure medications. I will let Dr. (Name) know. Message clinician in Wake One.
- - If No, no action

“Yes” Response:

1. *Keep it up! Plus thumbs up emoji*

Self-monitoring phase:

1. *Have you been checking your BP? We'll be checking in tomorrow for results!*

“Yes” Response:

1. *Nice work!*

Additionally:

What was the top number (SBP)?

What was the bottom number (DBP)?

“No” Response:

1. *Never too late to start! Try checking your BP in the AM and PM every day for the next few days and we'll check back again later.*

Data Response/Gamification:

1. *BP measurements received. You're doing great! Keep it up – you're currently in X place among texters.*

An adapted version of the System Usability Scale (SUS) by Bangor⁹ will be administered either in person or the phone after the follow up clinic visit or at the end of week 12 (if patient misses follow up appointment).

Study team members will perform the following tasks to track study participants progress:

Protocol version: 4.30.2020

1. Weekly tracking of number of patients contacted and who responded to SMS, number of SMS questions answered, and number of office visits completed
2. Monthly tracking of patient satisfaction surveys
3. Monthly reports distributed via email to the team providing ongoing feedback on performance related to patient outreach and patient satisfaction
4. When high or low BP is reported SBP > 180 or <90 and or DBP > 110 or <60, a study team member will send a message in Wake One to the clinic triage nurses. The triage nurse will contact the patient to arrange a clinician office visit or a nurse blood pressure check appointment based on additional information on clinical symptoms.

Outcome Measure(s)

A- Feasibility

Feasibility will be assessed consistent with the recommendations of Leon and colleagues.²⁴

Specifically, we will examine:

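### The praise-and-rank reply to a texted BP reading has no condition on the value, so an alert-range report can draw praise alongside the prompt to contact the clinic

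*Combined protocol and SAP*

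**What the plan says.** The message script stands under Interventions and Interactions. A participant who confirms checking BP at home is asked for the systolic and then the diastolic value. Under the sub-heading Data Response/Gamification, one reply follows: "BP measurements received. You're doing great! Keep it up", completed by the participant's current place among those texting. No second version is given for high or low readings.

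The alert rule stands under Methods and Measures, Design. "The threshold range set for SBP is between 90 and 180 mm Hg and between 60 and 110 mm Hg for DBP". Outside that range the clinician is alerted through the electronic record and "the patient will be sent an SMS and prompted to contact their clinic". The same section explains the limits by guidelines that "designate a hypertensive urgency to be 180/110 mm Hg or higher and hypotension 90/60 or lower".

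Item 4 of the tracking tasks, after the script, adds a staff action. "When high or low BP is reported SBP > 180 or <90 and or DBP > 110 or <60", a study team member messages the triage nurses, and "The triage nurse will contact the patient to arrange a clinician office visit or a nurse blood pressure check appointment".

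On who sends the texts, Design says "Text messages will be generated by Twilio platform", while Interventions and Interactions says that study team members send them.

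**The concern.** The only stated trigger for the praise reply is that values have arrived. An alert-range report therefore meets that trigger as well as the trigger for the clinic-contact SMS. The participant sees the text and not the sub-heading above it, so praise that arrives straight after the numbers can be taken as a comment on them.

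What is at stake is how clear one message is at a step that matters for safety. The clinic-contact SMS asks the participant to act. Reassurance next to it can dilute that request. The protocol selects participants for non-adherence and for being Black, Hispanic or of limited schooling, and its Background counts low literacy in its definition of vulnerable. The pilot also tests the tool ahead of a larger efficacy trial, so it is a sensible time to settle the script.

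**Working it through.** This is a check of message logic. There is no planned figure to reproduce.

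**Step 1: does the reply depend on the value?** Other parts of the script do branch. The adherence dialogue separates yes from no, then prescription filled from not filled, then side effects from none, with a phone call and a clinician message for the problem answers. The reply to BP values has no branch.

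**Step 2: is there a rule of precedence?** The clinic-contact SMS is required under Design but does not appear in the script, and its wording is not given. Neither Design nor Interventions and Interactions, including item 4, says that it replaces, precedes or suppresses the praise reply.

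**Step 3: run readings through the rules as written.**

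| Texted reading (mm Hg) | Scripted reply | Clinic-contact SMS (Design) | Nurse message (item 4) | Protocol's own label |
|---|---|---|---|---|
| 190/115 | praise and rank | yes | yes | urgency |
| exactly 180/110 | praise and rank | unclear: the range does not say on which side its end points fall | no: strict inequalities | urgency |
| exactly 90/60 | praise and rank | unclear, same reason | no: strict inequalities | hypotension |

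The first row is the point: both texts can go to the same person. The other two rows show a boundary gap that bears on the fix. A condition built on item 4 as worded would still send praise for the very values that Design labels urgency and hypotension.

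**Step 4: can the number of affected replies be stated?** It would be the number of BP reports times the chance that a report is in the alert range. The SMS arm has 24/2 = 12 participants. The first hypothesis is that "over 50% of contacted patients will respond to SMS messages and over 50% will check HBPM", but this does not fix the number of reports per person. The chance per report is not given at all. As an illustration only, take 12 independent reports. The chance of at least one in the alert range is 1 − (1 − p)^12, which is 11.4% at an assumed p of 1% and 71.8% at an assumed 10%. A range that wide supports no count.

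**Step 5: is any endpoint touched?** Anyone who triggers this reply has already sent the BP measurement that the Analytical Plan requires for the primary analysis. No outcome definition, test or sample size refers to the content of the reply.

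**The case against.** The strongest reply is that the praise is plainly for reporting. The sub-heading pairs data response with gamification, the message opens by confirming receipt, the rank is among texters, and no BP level is mentioned. Elsewhere the script also praises behaviour: checking BP and taking medication. Thanking someone for a report and asking that person to call the clinic are compatible. This stands. A reader might infer that the two texts contradict each other, and the documents do not support that. The message is mixed, and that a participant would misread it is a possibility the documents do not test.

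The script is also an outline. It omits the clinic-contact SMS that Design requires, so it may omit other branches, and staff who send texts could hold the praise back. This stands in part: the text shows that praise *can* be sent, not that it *will* be. But no written rule tells staff or platform to withhold it.

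A reader might further infer a serious safety gap. The documents do not support that either. The clinician alert, the SMS prompt and the nurse contact all remain in place, so follow-up is not lost.

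Last, removing praise takes away reinforcement for the behaviour that the engagement outcome measures. This is a fair objection to silence as a reply, and the fix below allows for it.

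**Conclusion.** The point holds as a minor, inexpensive improvement. Followed as written, the script lets an alert-range report draw praise and rank alongside a prompt to contact the clinic, and no rule settles which text should go.

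The conclusion rests on the written text alone and assumes that no undocumented rule in the platform or among staff suppresses the praise. The size is left open. A reader might infer that such replies are rare, or that they occur only in the first week. Neither is established. The first-week label stands directly above the adherence checkpoint, and it is unclear whether it also governs the later sub-headings on self-monitoring and data response. Texting continues every week for four weeks and fortnightly after that, and participants are asked to measure at least twice a week.

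**What to change.** Add one condition to the data reply. When SBP is ≥180 or ≤90, or DBP is ≥110 or ≤60 mm Hg, replace the praise and rank text with a neutral acknowledgement, such as *BP measurements received, thank you*, combined with the clinic-contact prompt that Design already requires, in English or Spanish. The limits are inclusive so that they match the definitions of urgency and hypotension under Design.

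Apply the same inclusive limits to the alert rule under Design and to item 4 of the tracking tasks, so that boundary readings are handled alike everywhere. Let the report still count toward the participant's rank. Replies to in-range readings stay as they are.

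The cost is an IRB wording amendment, a few more alerts for boundary values, and slightly less positive reinforcement on the affected reports. Item 4 already has a study team member act on out-of-range values, so no new staff role or study visit is needed.

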1. Screening: we will track the number of patients screened per month, the number enrolled per month, the proportion that are eligible who enroll.
2. Recruitment: number of participants who refuse to participate in the pilot at the time of recruitment and the reason why. Proportion of vulnerable patients screened but excluded because they did not own a phone with SMS capability.
3. Retention: the proportion of participants who continue to use the myHealth tool per month through three months will be tracked for the intervention.
4. Engagement: 12- SMS rate response of at least one home BP measurement. We will use 44% as our cut off based on an SMS study by Peters and colleagues²⁵.

Finally, we will monitor time needed for assessments and gather feedback on the participant burden.

B-Acceptability

Participants will complete the SUS in person on an I-Pad or over the phone. They will also be offered the opportunity to comment in their questionnaires about their experiences of taking part in the pilot. The SUS yields a single score on a scale of 0–100. A SUS score above a 68 would be considered above average. We will consider acceptable when >70 % of participants score the SUS above 68.²⁶

Secondary measures of interest

Medication adherence (MA) will be measured by administrating the four-item MAQ by the study coordinator during enrollment and at 3 months follow up visit. The MAQ was selected because it has been well-validated to identify adherence in HTN and scores have been shown to correlate well with a range of objective adherence measures.^{11,12}

SBP and DBP change at 3 months. BP will be measured during initial and follow up office visits by nurses or clinicians while patient is seated with automated arm devices according to standard office procedures. We will extract from the electronic medical record, SBP and DBP at enrollment and at 12 weeks follow up. The average change will be calculated and reported in mmHg.

No-show rate at 3 months' follow-up (f/u) clinic visits. If participants fail to come to their f/u visits within 7 days of their scheduled follow-up appointment, they will be considered as "no-shows". Our current clinic no-show rate is 30%, therefore if the study participants no-show rate is less than 30% we will consider our tool a feasible intervention.

Analytical Plan

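### The triage-nurse alert uses strict limits, so a texted 180/110 or 90/60, the two readings named in its stated basis, sends no nurse message

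*Combined protocol and SAP*

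**What the plan says.** Three statements bear on the alert.

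- **Task 4** (Interventions and Interactions, list of tracking tasks) gives the operating rule for the triage nurses: "When high or low BP is reported SBP > 180 or <90 and or DBP > 110 or <60". A study team member messages the nurses, who then contact the patient.
- **Methods and Measures, Design** describes an in-basket alert to the clinician and an SMS to the patient "if the participants report BP outside the threshold range". It defines the range thus: "The threshold range set for SBP is between 90 and 180 mm Hg and between 60 and 110 mm Hg for DBP", for a single measurement.
- **The same section gives the basis**: "These thresholds are made based on the" recommendations of hypertension guidelines, "which designate a hypertensive urgency to be 180/110 mm Hg or higher and hypotension 90/60 or lower".

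**The concern.** The basis includes its limits and the task 4 rule excludes them. The two pairs that the basis names are therefore readings on which the rule does not act. This rule decides whether the nurses are told about a texted reading between visits, so staff need one unambiguous version of it. The sponsor also intends the pilot to inform a later efficacy trial, and an uncorrected mismatch could carry forward.

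**Working it through.** The plan gives no figure to reproduce. The check has three parts.

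**1. The rule against its basis.** Rule: SBP > 180 or < 90, and/or DBP > 110 or < 60. Basis: 180/110 or higher, 90/60 or lower.

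| Reading | Task 4, either component | Task 4, both components | Basis (inclusive), both components | Basis (inclusive), either component |
|---|---|---|---|---|
| 180/110 | no | no | yes | yes |
| 90/60 | no | no | yes | yes |
| 181/110, 180/111, 89/60, 90/59 | yes | no | yes | yes |
| 180/100, 170/110, 90/70, 100/60 | no | no | no | yes |

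The first two rows hold however the and/or in task 4 is read, and whether the basis means both components or either one. The rest below takes task 4 as firing on either component, which is its natural sense.

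**2. How many whole-number readings are affected.**
- If the basis means both components: exactly two, 180/110 and 90/60.
- If either component is enough: every reading on the edge of the rectangle SBP 90–180, DBP 60–110. The edge has 91 × 51 − 89 × 49 = 4641 − 4361 = 280 points. Of these, 41 have DBP at or above SBP: 21 with SBP 90 and DBP 90–110, and 20 with DBP 110 and SBP 91–110. That leaves 280 − 41 = 239 with SBP above DBP.

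Only the two pairs are certain misses.

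**3. How often this would happen.** Inputs:
- 12 SMS-arm participants, reading Sample Size ("We will randomize 12 patients into 2 groups") as 12 per group, since the total is 24.
- 8 message rounds, from the schedule "weekly for four weeks and then every other week until their next appointment" if it runs 12 weeks (weeks 1–4, 6, 8, 10, 12).
- Assumed: one reading per round and full response, giving 12 × 8 = 96 readings.
- Assumed, because the documents give no distribution: SBP and DBP bivariate normal, rounded to whole numbers, correlation 0.5 to 0.7.

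Expected count = 96 × the summed probability of the relevant whole-number cells:

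| SBP mean/SD, DBP mean/SD | Missed, both components | Missed, either component | Alerts under current rule | Isolated DBP 60, share of either-component misses |
|---|---|---|---|---|
| 145/15, 80/12 | 0.0021–0.0038 | 1.06–1.08 | 5.4–5.5 | 74–75% |
| 145/15, 88/12 | 0.0049–0.0076 | 0.87–0.91 | 4.2–4.4 | 23–24% |
| 150/20, 88/12 | 0.0114–0.0168 | 1.12–1.23 | 8.4–9.0 | 17–18% |
| 150/20, 80/12 | 0.0039–0.0045 | 1.46–1.49 | 10.5–10.7 | 53–54% |
| 130/18, 75/12 | 0.0072–0.0085 | 1.56–1.60 | 10.1–10.4 | 88–91% |
| 130/18, 80/12 | 0.0064–0.0098 | 1.01–1.06 | 5.4–5.7 | 71–73% |

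The counts scale with the number of readings:
- If the 2-week nurse visit is the next appointment, there are about 2 rounds, or 12 × 2 = 24 readings. Misses fall to 0.0005–0.004 (both) or 0.22–0.40 (either).
- At 44% response, 0.44 × 96 = 42 readings: 0.0009–0.0074 (both) or 0.38–0.70 (either). The 44% is the engagement criterion under Outcome Measures ("We will use 44% as our cut off"). The plan does not define it as a response rate per round, so this case is only an illustration.

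**The case against.** The case on the other side has four parts.

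- **A reader might infer that 180/110 and 90/60 trigger no action at all. The documents do not support that.** The Design section's alert to the clinician and SMS to the patient are separate actions, and *between* can be read with or without its endpoints. If the endpoints are in range, which is the ordinary sense, that section agrees with task 4 and neither alert fires. If they are out of range, the Design alert fires and the nurse message does not. Only the missing nurse message is certain. This stands and limits the point, but either reading leaves text to correct.
- **Limits based on a guideline need not copy its inequality signs.** This is fair as far as it goes. If the basis means both components, the rule is otherwise broader than its basis: 4.2 to 10.7 alerts per 96 readings, against 0.1 to 1.9 readings that meet the inclusive two-component definition. Even so, the plan gives no reason for leaving out the two pairs it names.
- **Inclusive signs on every component go further than the two certain misses require.** This is true if the basis means both components. However, task 4 and the Design range already set limits for each component separately, so inclusive limits for each component are coherent.
- **The frequencies rest on assumptions.** This stands. Participants may also round the numbers they text, which could raise the counts at 180, 110, 90 and 60; the model ignores this.

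**Conclusion.** The mismatch is real and minor. As written, task 4 sends no triage-nurse message for 180/110 or 90/60, and no other text clearly repairs this. Under the assumed distributions, with 96 readings and one per round, well under one reading is missed in the whole pilot if both components must meet the limit, and about one to two if either is enough. An earlier end to messaging or a lower response reduces both.

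Two further inferences should be resisted. The 239 edge readings are not all established misses, because the basis names pairs and does not say that one component suffices. Nor is there ground for claiming a meaningful risk to participants: nothing in the documents shows that 180 differs clinically from 181, and the 2-week nurse visit and 3-month clinician visit remain. Sample size, error rates and analysis are not affected.

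**What to change.** Make two wording changes.

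- Task 4: change the condition to SBP ≥ 180 or ≤ 90 and/or DBP ≥ 110 or ≤ 60.
- Design section: make the trigger a reported BP at or outside the limits of the threshold range.

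Both named readings then send a nurse message however the and/or is read, and the two alert statements agree.

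The cost is the edits, a briefing for the staff who send the messages, and about 0.9 to 1.6 extra nurse messages on top of 4.2 to 10.7 over the pilot, under the 96-reading assumptions. Where the Design alert does not already fire at the endpoints, the clinician and patient messages follow too. Many of the additions may be an isolated DBP of exactly 60 with SBP in range: 53% to 91% where mean DBP is 75 or 80, and 17% to 24% where it is 88. If the sponsor does not want those alerts, a narrower option is to add only the two named pairs to task 4 and still state the endpoints in the Design section.

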Results will be analyzed initially using descriptive statistics. Comparison between groups will be done using chi square tests for proportions, and t-tests for continuous variables. Regression analysis will be performed to identify independent outcome predictors. RedCap will be utilized to collect all patient data. Participant's demographics (including education level), co-morbidities, number of medications, number of blood pressure medications and BP numbers will be extracted from Wake One when available. Level of education will be confirmed verbally with each participant during consent process. Only one participant identifier will appear in the data collection forms.

The full analysis set will include participants who have responded to at least one SMS message post-randomization. Descriptive statistics will be computed for each treatment group; medians and percentiles will be reported for skewed continuous variables. For primary and secondary outcomes, descriptive statistics and 95% confidence intervals will be used to summarize the differences between groups. The secondary outcome of BP and other continuous variables will be assessed with a repeated-measures analysis using a mixed linear model approach. The Wilcoxon rank sum test will be used to compare MA between groups. Hypothesis tests will be 2-sided using the 0.05 significance level. Bonferroni-type adjustments for multiple testing will be implemented to control type I errors. Statistical analysis will be performed using SAS software (SAS Institute, Cary, NC).

Treatment assignment will be determined using blocked randomization

The primary analysis will consist of all subjects who responded with at least one BP measurement

Human Subjects Protection

Subject Recruitment Methods

Subjects will be identified when they come to an office visit and their blood pressure is not well controlled. The PI clinician (internal medicine preceptors or residents) will verbally alert the study coordinator on site of possible participants based on BP >140/90. The study team member will meet the patient in a private room in 7th Janeway, determine eligibility, and signed informed consent will be obtained from each subject. Once enrolled, the subjects will be contacted by phone via SMS and phone call. To ensure equal access to participation among women and minorities we will translate all materials and questions to Spanish. The privacy of

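### The 44% engagement cut-off has no stated denominator and is 100% by construction if the plan's primary analysis set is applied to it; Aim 2 also gives 24 SMS participants where the design gives about 12

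*Combined protocol and SAP*

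**What the plan says.** **Engagement criterion.** Outcome Measure(s), A (Feasibility), item 4: "Engagement: 12- SMS rate response of at least one home BP measurement. We will use 44% as our cut off". The cut-off is taken from a cited SMS study. No base is named. The 12 with a trailing hyphen has no unit and may be text lost in the PDF conversion.

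**Analysis sets.** The Analytical Plan defines two sets, each by response. The full set: "The full analysis set will include participants who have responded to at least one SMS message post-randomization". The primary one: "The primary analysis will consist of all subjects who responded with at least one BP measurement". The same section says: "For primary and secondary outcomes, descriptive statistics and 95% confidence intervals will be used to summarize the differences between groups". No sentence says which set, if either, governs engagement.

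**Which outcomes are primary.** Adherence, blood pressure change and no-shows come under the heading "Secondary measures of interest". That leaves feasibility and acceptability as the primary outcomes, although the plan does not say so outright.

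**Size of the SMS arm.** Specific Aims, Aim 2: "One cohort of 24 participants will be recruited for the SMS intervention". Methods and Measures, Design: "A randomized control trial of 24 non-adherent participants will be monitored and followed for 3 months". Sample Size gives 24 patients and adds: "We will randomize 12 patients into 2 groups". The Design section describes an SMS arm and a control arm, and the control arm gets usual education and monitoring only.

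**The concern.** Engagement is the only one of the four items listed under Feasibility that carries a numeric cut-off, and the pilot's results are meant to support an application for an efficacy trial. Someone analysing the trial has to choose a denominator, and the plan offers a set called primary for an outcome that appears to be primary. That set consists of the people who met the engagement criterion, so using it turns the criterion into a tautology. The full analysis set is less extreme but works in the same direction: those who never answer are the clearest failures of engagement, and they leave the denominator.

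Aim 2's figure is a plain inconsistency. Only participants assigned to SMS receive texts and can reply to them. A reader who takes the arm size from Aim 2 starts from twice the number that the design provides.

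**Working it through.** **Inputs.** Total randomised 24, two arms (Design, Sample Size). Cut-off 44% (Feasibility, item 4). Set definitions from the Analytical Plan. Assumptions: equal allocation, which the plan implies but does not state; engagement read as the share of participants who text at least one home reading by week 12; everyone who texts a reading also counts as having answered an SMS.

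**Arm size.** 24 / 2 = 12 per arm, and 2 × 12 = 24 reproduces the stated total. Aim 2's 24 in the SMS intervention does not reproduce. The Sample Size sentence could literally be read as 12 people split in two, or 6 per arm, but no reading of it puts 24 in the SMS arm.

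**Smallest count that reaches 44%, by denominator.**

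| Denominator | 0.44 × n | Count needed |
|---|---|---|
| All 12 randomised to SMS | 5.28 | 6 |
| Full analysis set of 11 (assumed) | 4.84 | 5 |
| Full analysis set of 10 (assumed) | 4.40 | 5 |
| Full analysis set of 9 (assumed) | 3.96 | 4 |
| Full analysis set of 8 (assumed) | 3.52 | 4 |
| Primary set of any size k | k/k = 100% | 1 |
| Aim 2's 24 used as the base | 10.56 | 11 |

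In the last row, 11 of the 12 people who actually receive texts would have to respond.

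**Same data, different verdicts.** Suppose 5 participants text a reading:
- 5/12 = 41.7%: misses.
- 5/11 = 45.5%, 5/10 = 50.0%, 5/9 = 55.6%, 5/8 = 62.5%: each meets.
- 5/5 = 100%: meets.

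**Chance of meeting the cut-off.** The true rate is not in the documents, so a range is shown. On all 12 randomised to SMS, P(X ≥ 6) for a binomial with n = 12 is 0.118 at a true rate of 30%, 0.445 at 44%, 0.613 at 50% and 0.842 at 60%. On the primary set it is only the chance that at least one of 12 people replies: 1 − 0.70^12 = 0.986 at 30%, and higher at the other rates.

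**Precision on the true arm size.** The exact (Clopper-Pearson) 95% interval for 6/12 is 21.1% to 78.9%.

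**Per-message reading.** If the rate is replies over texts sent, the schedule under Interventions and Interactions (weekly for four weeks, then fortnightly) gives about 8 sends per person if it runs to week 12. That is 12 × 8 = 96 sends, and 0.44 × 96 = 42.24, so 43 replies are needed. The counts in the table do not apply to this reading. Nor is the primary set automatically 100%: one reading in 8 contacts is 1/8 = 12.5%.

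**The case against.** The 100% result needs three readings at once: the primary set governs feasibility, the qualifying blood pressure reading is one sent by SMS, and the rate is per participant. The Analytical Plan is also written around differences between groups, whereas engagement exists in one arm only. A sensible analyst might never use that set for engagement. This stands, and it makes the 100% conditional. It does not supply the missing denominator.

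A base can also be found nearby. The first hypothesis speaks of contacted patients, and the weekly tracking list counts patients contacted and those who responded. If everyone in the SMS arm is contacted, that base is the same 12. But the hypothesis carries a different figure (over 50%) and is not tied to the 44% rule. It is the nearest candidate, not a definition.

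On Aim 2, the Design and Sample Size sections make the two-arm structure clear, so the correction is editorial. That is fair. A reader might infer that the plan claims more precision than 12 participants allow. The documents do not support this: no interval, power or precision statement is computed from 24.

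A restored 12-week label in item 4 would settle the time window but not the base.

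**Conclusion.** The point holds in two parts. First, Aim 2's 24 SMS participants contradicts a design that randomises 24 in total, about 12 to SMS. Second, the 44% cut-off has no denominator, and the plan's only defined analysis sets are conditioned on response. Depending on the base, the number of people who must text a reading is 6, 4 or 5, or 1. The result therefore depends on a choice that the plan leaves open.

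A reader might infer that the plan instructs a circular analysis that guarantees success. It does not: no section assigns the primary set to engagement, and none excludes it. The 100% figure rests on that set being used, on a per-participant rate and on readings returned by SMS. The counts also rest on 12 per arm and, for the full analysis set, on an assumed 8 to 11 people answering any text. The missing denominator and the Aim 2 figure rest on none of these readings.

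**What to change.** 1. Correct Aim 2 to 24 randomised, 12 of them to SMS.
2. Define engagement as the number of participants who text at least one home blood pressure reading within 12 weeks, divided by all participants randomised to SMS. Count non-responders as not engaged. State the count: at least 6 of 12 to reach 44%.
3. State that neither responder-defined set in the Analytical Plan applies to engagement.
4. Report the exact 95% interval on 12 with the result.
5. If wanted, show the contacted-patients figure (over 50%) alongside, labelled as a separate expectation.

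The cost is wording. The tracking already planned records who was contacted and who responded, and the texts themselves ask for the readings. The criterion becomes harder to meet than on a responder denominator, the interval on 12 is wide, and the protocol change must be reported to the IRB under the plan's own reporting section.
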